1.5.4 Germany

	Screening Visit*	Visit 0	Visit 1	Visit 2	Visit 3	Visit 4	Visit 5	Visit 6	Visit 7	Early
Study Day	Day -35*	Day -28	Day 0	Day 28	Day 56	Day 168	Day 196	Day 224	Day 286	Termination
Time windows / treatment groups	M1+M2: -35 to -29 A-D: -7 to -1	M1+M2: ±5 days **A-D -28 is study day (M1+M2 day 0 = V0+V1 at once on d 0	±5 days all groups	± 5 days all groups	±10 days only M1+M2	± 10 days all groups	± 10 days all groups	± 10 days all groups	
Informed consent	Х									
Inclusion/exclusion criteria (1)	Х	Х	X (14)	Х	Х	X (14)	X			
HIV, hepatitis B/C, [blood: 8-10 mL]	Х									
Demographic data	Х									
Physical examination	X									
Vaccination history	X									
Hematology blood sample [3-5 mL] (6)	X				X			Х		X
Coagulation parameter [blood: 3-5 mL] (7)	Х				Х			Х		Х
Clinical chemistry serum [8-10 mL] (8)	Х				Х			Х		Х
Urinalysis (10)	Х				X			Х		X
Medical history	X	X (2)								
Concomitant medications	Х	Х	X (14)	Х	Х	X (14)	X	Х		X
Assessment of arthralgia	X	Х	X (14)	Х	X	X (14)	X	X		X
Symptom-directed physical exam (3)		Х	X (14)	Х	X	X (14)	X	Х	0	X
Vital signs (4)	Х	Х	X (14)	Х	X	X (14)	X	X		X
Urine pregnancy test (9)	X	х	X (14)	Х	Х	X (14)	X	Х	(15)	X
Randomization	1	M1+M2 X AB	СР							
Study treatment: vaccination		X (14)	X	Х		X (14)	X			
Immunogenicity 1: serum [blood: 2x 8-10 mL]		X (14)	Х	х	х	X (14)	х	x		x
Immunogenicity 2 (5.1): [blood: 16-20 mL]		X (14)	X	Х	Х	X (14)	X	Х		Х
Measles antibody titer [no additional blood sample]		X (14)	х	Х	х					х
T- cell analysis (5.2): [blood: 24-30 mL]			Х	Х	X	X (14)	X	Х	1	Х
Measles virus shedding (13): [blood: 2-3 mL, urine and saliva]	5		X (13)	X (13)			X (13)			
Local tolerability (12)		X (14)	Х	X	X	X (14)	X	X		X
Dispense subject diary (11)		X (14)	х	х		X (14)	X			
Collect subject diary (11)	1		X (14)	Х	Х		X (14)	Х		X
Adverse events		X (14,2)	X (2)	х	Х	X (14)	X	X		Х

Screening visit within 7 days before randomization

(1) After randomization only exclusion criteria, which could influence the subject's eligibility throughout the study will be checked. The following exclusion criteria are concerned: 1, 7, 8, 10, 19, 20, 21, 22 and 23

Symptoms noted prior to randomization are not considered as adverse events but will be recorded as medical history

Including system-based assessment if necessary according to symptom-directed physical examination. (section 11.2.2)

(2) (3) (4) Systolic and diastolic blood pressure, body temperature and pulse

Sites outside of Vienna: serum samples (blood 2x 8-10 mL) to be collected for additional immunogenicity analyses (cross neutralization and passive transfer) Vienna sites only: PBMCs will be isolated from fresh blood (blood 24-30 mL and once at V3 48-60 mL). (section 8.3.2) (5.1)

(5.2)

(6) (8) Hemoglobin, hematocrit, erythrocyte count, differential white blood count, platelets (EDTA blood; 3-5 mL) (7) Prothrombin time, aPTT, fibrinogen (blood: 3-5mL)

Creatinine, sodium, potassium, calcium, aspartate aminotransferase (AST), alanine aminotransferase (ALT), alkaline phosphatase, bilirubin (blood 8-10 mL),

(9) Pregnancy test will be performed for women of childbearing potential. (section 8.3.6)

Glucose, protein, pH, erythrocytes, leucocytes, nitrite, ketones, urobilinogen, bilirubin and specific gravity (10)

The subjects will assess local tolerability and systemic reactions themselves over a period of 7 consecutive days after each injection. (section 11.2.5) (11)

(12) Investigation of injection site reaction 1 hour after vaccination and additionally before each subsequent vaccination. (section 11.2.4)

(13) Shedding: only in AKH Vienna, only in a subset of group A-D, on day 0, 28, 196 and additional shedding sampling visits on day 7, 10 and 14 (±1 day each) after the first vaccination on day 0. (section 8.3.1)

(14) Only measles booster group M1 and M2

(15) women of childbearing potential will be followed up by a phone call, to ensure no pregnancy occurred 3 months after the last vaccination

Group A, B, C, and D will perform Visit 0 and Visit 1 procedures on one day, group M1 and M2 will perform V0 and V1 on two days (28 days apart) **

SAP (MV-CHIK-202, FINAL 3.0, 09-May-2018)

Based on:

STAT03 A Statistical Analysis Plan

Version 5.0, Effective Date 16-Dec-2016

Confidential and intellectual property of Assign DMB. No part of this document or its contents may be duplicated, referenced, published or otherwise disclosed in any form or by any means without prior written consent of Assign DMB.

Page 14 of 47

2. GENERAL CONSIDERATIONS

The Statistical Analysis Plan (SAP) is based on the final study protocols for Austria (Version 1.5; 24-Nov-2016) and Germany (Version 1.6; 19-Apr-2017). The present Statistical Analysis Plan (SAP) has been prepared in order to pre-specify and describe the statistical analyses that will be performed for the DSMB Analysis, the Preliminary Analysis and the Final Analysis. The analysis plan will be signed off before database snapshot for the DSMB Analysis.

2.1 Rationale

This Phase 2 trial is designed to investigate the immunogenicity, safety and tolerability of MV-CHIK.

Two different doses of MV-CHIK at a concentration of $5x10^4$ (± 0.5 log) TCID₅₀/ dose and $5x10^5$ (± 0.5 log) TCID₅₀/ dose per 0.3 mL will be assessed to healthy adults for the induction of functional anti-chikungunya neutralizing antibodies. In addition, the direct effect of the pre-existing vector immunity will be addressed by the immunization of a small subset of subjects with Priorix® prior immunization with two doses of MV-CHIK.

2.2 Conduct of Analysis

2.2.1 Preliminary Analysis

A preliminary analysis including safety and immunogenicity data will be performed in August 2017. The analysis was initially planned to be conducted after all subjects completed Visit 3 (Day 56) but was re-scheduled due to unforeseen delays to enable further vaccine development progress. The goal of this analysis is to provide highly valuable data of the novel Chikungunya vaccine for further development. Results from this analysis will have no impact on the study design and treatment of the subjects in this study.

All tables and listings marked with an "x" in column "IA" in section 10.1 and 10.1 will be generated for this Preliminary Analysis.

2.2.2 Final Analysis

The final analysis will be conducted once the last subject has completed the study.

All tables and listings marked with an "x" in column "FA" in section 10.1 and 10.1 will be generated for this Final Analysis.

2.3 Treatment Groups

For tables the groups M1 and M2 are not stratified by country (Austria, Germany):

- M1 of Austria (low dose) and M1 of Germany (high dose) are summarized in one group M1
- M2 of Austria (low dose) and M2 of Germany (high dose) are summarized in one group M2

Following treatment groups will be used in the analysis:

1. Group CV1: control vaccine on Day 0 and 28

SAP (MV-CHIK-202, FINAL 3.0, 09-May-2018) Page 15 of 47 Based on: STAT03_A Statistical Analysis Plan Version 5.0, Effective Date 16-Dec-2016 Confidential and intellectual property of Assign DMB. No part of this document or its contents may be duplicated, referenced, published or otherwise disclosed in any form or by any means without prior written consent of Assign DMB.

- 2. Group CV2: control vaccine on Day 28 and 196
- 3. Group A: MV-CHIK low dose on Day 0 and 28
- 4. Group B: MV-CHIK low dose Day 28 and 196
- 5. Group C: MV-CHIK high dose on Day 0 and 28
- 6. Group D: MV-CHIK high dose Day 28 and 196
- 7. Group M1: MV-CHIK on Day 0 and 28
- 8. Group M2: MV-CHIK on Day 168 and 196

Further, tables will show one total column for

- 9. all MV-CHIK serum groups (i.e. total of A, B, C, D, M1 and M2)
- 10. all control vaccines (i.e. total of CV1 and CV2)

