### 6.3 Randomization

At Visit 0, eligible subjects will be assigned to one of six treatment groups in timely order and receive a three-digit randomization number using randomization envelopes provided by data management. The site will also be provided with emergency envelopes for unblinding in case of emergency and if knowledge of the treatment assignment is mandatory for emergency treatment.

Treatment groups A, B, C and D:

All subjects will receive three i.m. injections on study day 0, 28 and 196. Subjects randomly allocated to group A or B will receive either MV-CHIK low dose or a control-vaccine (Priorix® or MMR-Vax-Pro® or equal measles vaccine). Subjects randomly allocated to group C or D will receive MV-CHIK high dose or a control-vaccine. Block randomization will be used with a randomization ratio of 1:6 (control-vaccine : MV-CHIK).

All subjects of treatment groups A, B, C and D additionally will be randomized to one of two treatment sequences. Group A + C will receive vaccinations (MV-CHIK or control vaccine) on day 0 and 28 and placebo injection on day 196 whereas groups B + D receive placebo injection on day 0 and vaccinations (MV-CHIK or control vaccine) on day 28 and 196.

Measles booster group M1 and M2:

All subjects will receive five i.m. injections and the first injection on day -28 will be the control vaccine (Priorix® or MMR-Vax-Pro® or an equal measles vaccine). Subjects will be randomly allocated to receive MV-CHIK on day 0 and on 28 (and placebo on day 168 and 196), or to receive MV-CHIK on day 168 and on 196 (and placebo on day 0 and 28). Randomization ratio between the two booster groups will be M1 : M2 = 1 : 1

Randomization of 320 subjects to one of the six treatment groups:

Group A: MV-CHIK low : control-vaccine = 60 : 10

Group B: MV-CHIK low : control-vaccine = 60 : 10

Group C: MV-CHIK high : control-vaccine = 60 : 10

Group D: MV-CHIK high : control-vaccine = 60 : 10

Group M1:M2 MV-CHIK high day 0+28 : MV-CHIK high day 168+196 = 20 : 20

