### 13.2 Safety Analysis

Solicited AEs (reactogenicity): Solicited local and solicited systemic AEs will be summarized for the 7 day period, by AE grade (mild, moderate, severe), by group and by dose. Solicited AEs will not be coded into MedDRA or assessed for relatedness. The number and percentage of subjects with AEs will be presented. Subjects who reported data for a solicited event at any time point during the time period summarized would be included in the denominator for that event. Thus, denominators for each solicited event will not include subjects who were missing all data for that event, during the time period summarized. P-values for AE rates for MV-CHIK vs. Priorix® (or equal control-vaccine), for the same schedule, will be provided in summary tables (pairwise comparisons).

Unsolicited AEs: Separately, the number and percentage of subjects with unsolicited treatment emergent adverse events (TEAEs), medically-attended AEs (MAEs) and serious adverse events (SAEs) will be presented for each treatment group overall and by system organ class/preferred term, and by AE grade, and relatedness. All SAEs and MAEs are also included in TEAE tables. Arthritis AEs, AEs of special interest (AESI), will be included in the TEAE tables. For unsolicited AEs, all subjects entered into the study who receive at least one vaccination will be included in the safety analysis based on the product received (“as treated”), for the time period summarized. P-values for AE rates for MV-CHIK vs. Priorix®, for the same schedule, will be provided in summary tables (pairwise comparisons).

Unsolicited AEs and concomitant diseases will be coded using the MedDRA coding dictionary; concomitant medications will be coded using the WHO Drug Dictionary.

Solicited and unsolicited AEs (local and systemic), MAE, SAE and AESI (arthralgia) will be recorded up to Visit 6 (day 224).

Safety analyses will be performed by means of descriptive measures. Laboratory values will be assigned a grade. Changes in laboratory values and grades as well as vital signs from study entry to end of treatment/follow up will be analyzed descriptively.

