All subjects of the measles booster group M1 and M2 will receive five i.m. injections on study day -28, 0, 28, 168 and 196. The first vaccination will be Priorix® or equivalent measles vaccine on study day -28. Group M1 will receive MV-CHIK low/high dose vaccinations on day 0 and day 28 and placebo on day 168 and 196. Group M2 will receive placebo on day 0 and 28 and MV-CHIK low/high dose on day 168 and on day 196.

Group A, B, C and D will be merged into a first category labeled as Group A/B/C/D. Group M1 and M2 will be merged into a second category labeled as Group M1/M2.

All subjects will be followed for safety and immunogenicity evaluation until day 224. The estimated study duration per subject will be 33-37 weeks (~8 months), respectively. Overall study duration is estimated to be 3 years from study initiation until reporting.

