1.3.2 Secondary Endpoints

• Immunogenicity on Day 0, 28, 196 and 224; additionally for group M1 and M2 on Day -28 and 168 as confirmed by the presence of functional anti-chikungunya antibodies as determined by the plaque reduction neutralization test (PRNT₅₀) and by ELISA.

- Measurement of anti-measles antibodies on day 0, 28, and 56; additionally for group M1 and M2 on day 28 as determined by ELISA.
- Solicited local and systemic adverse events (AEs)
- Serious adverse events (SAEs)
- Rate of AEs during the 28 day post-vaccination period
- Safety laboratory parameters (hematology, serum chemistry, urinalysis)
- Shedding of live recombinant virus until day 196 (subset of subjects)
- Induction of a Chikungunya virus specific T cell responses (subset of subjects)
- Pre-existing anti-vector immunity:
 - Immunogenicity of Chikungunya vaccine in the presence of recently boosted measles immunity (measles booster groups M1 and M2).
 - Relation of post-vaccination anti-chikungunya plaque reduction neutralization titers (PRNT₅₀) and baseline anti-measles ELISA titers (all treatment groups).

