2.7.3 Inferential Analysis for the Safety Analysis

A Fisher's exact test will be provided to compare the AE rates for MV-CHIK vs. Priorix®. P-values will also be provided to compare AE rates between treatment groups (pairwise comparisons). No adjustment for multiple testing will be performed.

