8.3 Adverse Events

Adverse Events are statistically analyzed once for the Preliminary Analysis up to Visit 3 and once for the final analysis.

The Preliminary Analysis includes all Adverse Events with a start date which is at of before the date of Visit 3. Adverse Events will be coded using the Medical Dictionary for Regulatory Activities (cp. section 2.15)

Solicited AEs comprise reactions at the injection site or systemic reactions that are typical for vaccinations:

- Solicited local AEs (injection site reactions) are the following: injection site pain, tenderness, pruritus, erythema (redness), edema, induration (hardening)
- Solicited systemic AEs are the following: headache, fever, myalgia, limb discomfort, arthralgia, flu-like symptoms, nausea, vomiting, rash and excessive fatigue.

For solicited local and systemic AEs were summarized for a 7 day period. Solicited AEs will not be coded into MedDRA and no assessment of relatedness was performed.

An AE is considered to be related to study drug if the "Causal relationship to study treatment" was considered "definite", "probable", "possible" or the classification is missing.

For solicited local and systemic AEs the following tables will be tabulated:

- at least one AE
- at least one serious AE
- at least one severe AE

SAP (MV-CHIK-202, FINAL 3.0, 09-May-2018) Page 32 of 47 Based on: STAT03_A Statistical Analysis Plan Version 5.0, Effective Date 16-Dec-2016 Confidential and intellectual property of Assign DMB. No part of this document or its contents may be duplicated, referenced, published or otherwise disclosed in any form or by any means without prior written consent of Assign DMB.

• at least one AE by severity

An AE is considered to be a treatment-emergent AE (TEAE) if, and only if, first onset or worsening is simultaneous with or after first vaccination (AE start date is greater or equal first vaccination date). AEs for which it cannot be clearly decided if the start date was before or on/after first vaccination will be considered treatment-emergent, following a worst case approach.

For unsolicited AEs the following tables will be tabulated:

- at least one TEAE
- at least one severe TEAE
- at least one serious TEAE
- at least one TEAE related to study drug
- at least one medically attended TEAE
- at least one TEAE where an action was taken (i.e. no action taken was NOT ticked)
- at least one TEAE of special interest (arthritis)

The same tables grouped by SOC and PT will be provided.

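### The SAP lists a 28-day adverse event rate but defines no analysis for it, and its MV-CHIK total column counts saline and MMR periods, including M2 before any MV-CHIK dose

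*SAP*

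**What the plan says.** Both documents list the 28-day rate among the secondary endpoints (Protocol 4.1.2, SAP 1.3.2): "Rate of AEs during the 28 day post-vaccination period".

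SAP 8.3 uses three time frames for adverse events, none of them 28 days:
- seven days for solicited events;
- everything up to Visit 3 for the preliminary analysis;
- an open-ended rule for unsolicited events, which are treatment-emergent if "first onset or worsening is simultaneous with or after first vaccination (AE start date is greater or equal first vaccination date". No end is given; Protocol 13.2 has events recorded up to Day 224.

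SAP 2.3 sets out eight analysis groups (CV1, CV2, A, B, C, D, M1, M2) and then says: "Further, tables will show one total column for" two pools. One is "all MV-CHIK serum groups (i.e. total of A, B, C, D, M1 and M2"; the other is CV1 with CV2.

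For inference, SAP 2.7.3 says that a Fisher's "exact test will be provided to compare the AE rates for MV-CHIK vs. Priorix". It adds pairwise p-values between groups without multiplicity adjustment. Protocol 13.2 is narrower: p-values for MV-CHIK against the control vaccine, "for the same schedule, will be provided in summary tables (pairwise comparisons". It also counts unsolicited events by the product received within the period being summarised.

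On exposure, SAP 1.2 states: "Group M2 will receive placebo on day 0 and 28 and MV-CHIK low/high dose on day 168 and on day 196". M1 and M2 both start with MMR on Day -28. B and D start with saline on Day 0.

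**The concern.** A listed endpoint for which the analysis plan gives no window, table or test will either go unreported or be defined after the data are seen. Safety is part of the primary objective, and SAP 2.17 declares no change to the protocol's planned analysis other than the timing of the preliminary analysis. This therefore reads as an omission and not as a decision.

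The total column adds a second difficulty. It is labelled MV-CHIK, but it is built from whole randomised groups. Events after saline or MMR enter it as MV-CHIK events. M1 and M2 receive five injections against three in the controls, and no control group shares their schedule, yet they enter the pooled comparison with control. At the preliminary analysis, which is meant to inform further development of the vaccine, one group in the column has not received the vaccine at all.

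**Working it through.** **Inputs.** Protocol 6.3 gives "Group A: MV-CHIK low : control-vaccine = 60 : 10", the same split for B, C and D, and 20 each for M1 and M2. Schedules are from Protocol Table 1 and SAP 1.2. Planned numbers, full adherence and nominal visit days are assumed throughout.

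**Plan's own total.** 4 × (60 + 10) + 2 × 20 = 320, as stated. The MV-CHIK column is 4 × 60 + 2 × 20 = 280; the control column is 4 × 10 = 40 (20 in CV1, 20 in CV2).

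**Injections in the MV-CHIK column**

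| Day | MV-CHIK | Saline | MMR |
|---|---|---|---|
| -28 | 0 | 0 | 40 |
| 0 | 140 (A, C, M1) | 140 (B, D, M2) | 0 |
| 28 | 260 | 20 (M2) | 0 |
| 168 | 20 (M2) | 20 (M1) | 0 |
| 196 | 140 (B, D, M2) | 140 (A, C, M1) | 0 |
| All | 560 | 320 | 40 |

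The total is 920, so 560/920 = 60.9% are MV-CHIK, 34.8% saline and 4.3% MMR. Up to Day 56 (rows -28, 0 and 28) the counts are 400, 160 and 40 of 600: 66.7%, 26.7% and 6.7%.

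**Person-time in the final column**
- Total: 240 × 224 + 40 × 252 = 53,760 + 10,080 = 63,840 days.
- Within 28 days after MV-CHIK: 280 × 56 = 15,680, or 24.6%.
- Within 28 days after any injection: 240 × 84 + 40 × 140 = 25,760, or 40.4%. So 59.6% lies outside every 28-day window.
- Before the subject's first MV-CHIK dose: B and D 120 × 28, M1 20 × 28, M2 20 × 196 = 3,360 + 560 + 3,920 = 7,840, or 12.3%.

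**M2 at the preliminary analysis.** By Day 56, M2 has had one MMR and two saline injections. That is 20/280 = 7.1% of the column; the exposed denominator is 260. The shift in a per-subject rate depends on rates that the documents do not give. Under assumed pairs for exposed and unexposed subjects:
- 30% and 10%: (260 × 0.30 + 20 × 0.10)/280 = 28.6% instead of 30%;
- 50% and 20%: 47.9% instead of 50%;
- 80% and 30%: 76.4% instead of 80%.

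**Balance of A to D against control.** Saline makes up 240 of 720 injections in A to D (33.3%) and 40 of 120 in the controls (33.3%). The share is the same, so the imbalance in the pooled comparison comes from M1 and M2.

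**Immunogenicity total at Day 28.** Before that day's injection, B, D and M2 have had no MV-CHIK: 60 + 60 + 20 = 140 of 280. At Day 56, 260 of 280 have had at least one dose.

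**The case against.** Several points in the plan's favour stand.

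- A reader might infer that the SAP has abandoned both as-treated analysis and same-schedule comparison. It has not. SAP 2.16 analyses the Safety population by the treatment actually given. What it omits is the protocol's link to the period summarised, and the preliminary safety analysis uses the mITT set, as randomised. CV1 and CV2 match the schedules of A/C and B/D, so the pairwise tests in SAP 2.7.3 already contain the protocol's contrasts. They are simply not singled out from the other unadjusted tests.
- A reader might infer that no safety table separates the products. The diary tables by diary period do so within each single-group column. They cover seven-day diary symptoms at the final analysis only, and do not address unsolicited events.
- For A to D, the preliminary cut at Visit 3 nominally equals the 28-day windows after Days 0 and 28 taken together. This comes close to the endpoint for those two injections, but it is neither labelled as the endpoint nor split by product.
- M2 is unexposed only at the preliminary analysis. By the final analysis its completers have had two doses, though their events from Day -28 to Day 168 still count under MV-CHIK.
- It is tempting to claim a large loss of power or a masked vaccine effect. The documents give neither a background event rate per 28 days nor an expected vaccine effect, so no power figure can be supported.
- No decision rule uses the total column, and Protocol 13.2 describes the safety analyses as descriptive.

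Text beside the SAP table list was not available for this review. The finding on the 28-day window therefore rests mainly on SAP 2.7.3 and 8.3, which describe none.

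**Conclusion.** The plan is wrong as written on two counts. First, a stated secondary endpoint has no defined analysis: the final unsolicited event tables use an open window, in which about 25% of person-time in the MV-CHIK total falls within 28 days after MV-CHIK. Second, the total column does not measure MV-CHIK exposure: 61% of its planned injections are MV-CHIK, and at the preliminary analysis 20 of its 280 subjects have received none.

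The documents do not support a charge of bias in A to D against control. That comparison is randomised with equal saline shares, so the open window there reduces sensitivity only. The numerical effect of misplacing M2 is modest under the assumed rates. The case for correction rests on the missing endpoint and the mislabelled column. The counts assume planned numbers, full adherence and nominal visit days.

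The Day 28 immunogenicity total, half of it unvaccinated with MV-CHIK, is a secondary matter because inference uses the eight separate groups.

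**What to change.** 1. Add to SAP 8.3 and the table list a table of unsolicited events with onset within 28 days after each injection, attributed to the product of that injection. State how an event is assigned when the next injection falls before 28 days have passed, for example to the most recent injection. Keep the whole-study table as supportive.
2. Do not count M2 as MV-CHIK before its first MV-CHIK dose. Base the pooled MV-CHIK against control comparison on A to D against CV1 plus CV2, and show M1 and M2 separately. State where subjects in B, D or M2 who leave before any MV-CHIK dose are placed.
3. In SAP 2.7.3, name A and C against CV1, and B and D against CV2, as the protocol's same-schedule comparisons.
4. As a lesser change, omit the pooled immunogenicity total at Day 28 or present it by number of MV-CHIK doses received.

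The cost is SAP wording and table programming. The SAP listings already include vaccination dates and event start dates, so no new data are needed.
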